## 4 STUDY DESIGN AND ENDPOINTS

### 4.1 DESCRIPTION OF THE STUDY DESIGN

This is an open-label, comparative, single-center study to evaluate the feasibility and safety of a LED device and a diode laser device for non-invasive lipolysis of the flanks.

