#### 4.2.2 SECONDARY ENDPOINTS

### Safety objectives

Subject's assessment of discomfort and pain as measured by a 10 cm visual analog scale (VAS).

Subjects experiencing a treatment-related adverse event (AE).

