#### **Treatment**

Based on the mild nature of treatment, anesthesia is not required. Treatment procedure should include positioning of the patient in a manner that enables access to the target treatment anatomical site. A water-based spray should be applied to the treatment area immediately prior to treatment.

Each subject will receive two consecutive treatments in the following order: the left flank of the abdomen will be treated with the diode laser device and the right flank of the abdomen will be treated with the LED device. The exact placement on the flank will be left to the principal investigator's judgement based on his assessment of individual subject requirements for treatment. Subjects will be treated on the same bilateral location with each device to ensure consistency of measurements. Both laser and LED applicators will be set to same output power level. Two levels will be used 41W (1.17W/cm^2) and 29W (0.83W/cm^2). The first level of 41W corresponds to initial heating for 4 minutes and the second level corresponds to duty cycle of 25 sec on and 10 sec off time. Total treatment time with each device will be 24 minutes (first 4 min at full power and next 16 min at duty cycle 25/10). Both device applicators have same output window dimensions and area 7x5 cm (35 cm^2). Both applicators are cooled by water chiller and therefore provided the same surface cooling temperature on skin.

Immediately (within 2 minutes) after treatment, 3 sterile thermocouple needles of different lengths (7-15 mm), will be inserted into the center of each applicator footprint. Temperature readings from each thermocouple needle will be recorded.

During treatment, subject reaction must be monitored and if the subjects verbally report an intolerable level of pain, treatment shall be ceased immediately.

The normal response to these treatments is transient erythema and edema. If any side effects occur other than a normal transient response, as indicated in the protocol, they will be recorded.

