### 8.2.2 RELATIONSHIP TO STUDY AGENT

The clinician’s assessment of an AE's relationship to the study agent is part of the documentation process, but it is not a factor in determining what is or is not reported in the study. If there is any doubt as to whether a clinical observation is an AE, the event should be reported. All AEs must have their relationship to study agent assessed. In a clinical trial, the study product must always be suspect. To help assess, the following guidelines are used.

- **Related** – The AE is known to occur with the study agent, there is a reasonable possibility that the study agent caused the AE, or there is a temporal relationship between the study agent and event. Reasonable possibility means that there is evidence to suggest a causal relationship between the study agent and the AE.
- **Not Related** – There is not a reasonable possibility that the administration of the study agent caused the event, there is no temporal relationship between the study agent and event onset, or an alternate etiology has been established.

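### The Related and Not Related definitions in section 8.2.2 overlap, and the text does not require adverse events to be attributed to a device, so the treatment-related AE endpoint is ambiguous

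*Combined protocol and SAP*

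**What the plan says.** Section 8.2.2 offers two categories. Related has three alternative routes: the event is a recognised effect of the agent, causation is a reasonable possibility, "or there is a temporal relationship between the study agent and event". The section then explains the second route: "Reasonable possibility means that there is evidence to suggest a causal relationship between the study agent and the AE". Timing is therefore a separate route that needs no causal evidence.

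Not Related also has three alternative routes. The first is "There is not a reasonable possibility that the administration of the study agent caused the event". The other two are "there is no temporal relationship between the study agent and event onset, or an alternate etiology has been established".

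The classification feeds a named safety endpoint. Section 4.2.2 gives it as "Subjects experiencing a treatment-related adverse event (AE"), and the Protocol Summary and section 3 repeat it. The Protocol Summary also makes comparison of safety between the two devices part of the objective.

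Section 4.1 describes the design: "This is an open-label, comparative, single-center study to evaluate the feasibility and safety of a LED device and a diode laser device". Under Treatment in section 7.3.2, sides are fixed, with the laser always on the left and the LED always on the right. The two treatments are consecutive. Within 2 minutes after treatment, three thermocouple needles go into the centre of each applicator footprint.

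Section 10.3 lists three AE summaries, each a number and percentage of subjects: any AE, any serious AE, and permanent withdrawal from treatment because of an AE.

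**The concern.** A two-category causality rating is usable only if each event falls in exactly one category. Here one event can satisfy both lines, and section 8.2.2 is the only text that says what related means for the endpoint. Two clinicians could apply the text correctly to the same event and give opposite ratings.

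The overlap is likely to matter in practice. Both treatments fall on one day and the scheduled follow-up is a telephone call within a week (section 7.3.3), so most recorded events can be called temporally related. That is a judgement; the documents give no event rates. The assessor knows which device treated which side, and no independent adjudication of relatedness is described.

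A second gap sits beside the first. Relatedness is judged against a single study agent or study product, while every subject is exposed to both devices. A count of subjects with an AE then describes the combined exposure, not either device.

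**Working it through.** The documents give no figure to reproduce: section 10.4 states that there is no formal sample size calculation. The check is one of logic plus one division.

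**Criteria, all from section 8.2.2**
- A: recognised effect of the agent
- B: reasonable possibility of causation
- C: temporal relationship
- D: alternate cause established

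**Literal reading**
- Related = A or B or C. It fails only when A, B and C are all absent, D being free: 2 combinations.
- Not Related = (not B) or (not C) or D. It fails only when B and C are present and D is absent, A being free: 2 combinations.
- No combination fails both, since that would need B both absent and present.
- Both categories: 16 − 2 − 2 = 12 combinations. Related only: 2. Not Related only: 2.
- With a temporal relationship (C present) there are 8 combinations. All are Related and 2 fail Not Related, so 6 of 8 are in both.

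**Do softer readings of Not Related remove the overlap?**

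| Reading of Not Related | Both | Related only | Not Related only | Neither |
|---|---|---|---|---|
| Any one route is enough (literal) | 12 | 2 | 2 | 0 |
| (not B and not C) or D | 8 | 6 | 2 | 0 |
| All three routes required | 1 | 13 | 1 | 1 |

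None of the three gives categories that are both exclusive and exhaustive. The entries count logical combinations and say nothing about how often each would occur.

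**A concrete case**
Six needles are inserted per subject (3 per footprint × 2 footprints). Purpura is among the expected events in section 8.2.3. Suppose a bruise is recorded as an AE and traced to a needle. It is of a recognised type (A) and close in time (C), so it is Related. If the needle counts as an alternate cause (D), it is also Not Related.

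**Size at the endpoint**
One subject reclassified: 1/10 = 10 percentage points at the maximum enrolment of 10.

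**Attribution by device**
Sections 8.3 and 8.4.1 list the AE items to collect: description, onset and resolution, severity, and relationship. Device and flank are not among them. The denominators in section 10.3 are subjects, and each subject contributes both devices.

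**A rule that closes the gap**
Let Not Related = (not B) or D, and Related otherwise, that is, B present and D absent. With A and C free this gives 2 × 2 = 4 combinations Related and 12 Not Related, with none in both and none in neither.

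**The case against.** The strongest reply is that little in the plan depends on the classification. Section 8.2.2 says relatedness does not decide what is reported, section 8.3 documents all AEs whatever the relationship, and section 8.4.2 requires SAE reports regardless of relatedness. None of the three AE summaries in section 10.3 uses it. This stands, and it limits the point to the treatment-related AE endpoint. It does not rescue that endpoint, which is named in three places and has no listed summary of its own.

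Section 8.2.2 also presents its lines as guidelines and tells the clinician always to suspect the study product. That leans towards Related in doubtful cases, but it sets no order of precedence and does not cancel the alternate-cause route.

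The needle example can be contested. Insertion is a protocol procedure, and the text does not say whether it is an alternate cause. Haemorrhage and purpura are in any case graded by the investigator and summarised without a causality rating. The example is therefore a possibility; the overlap does not depend on it.

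Two stronger readings are tempting:
- A reader might infer that needle marks alone could swing the rate from 0% to 100%. That assumes such marks are recorded as AEs in all 10 subjects and all rated the same way. The documents give no rate and do not say that needle marks count as AEs.
- A reader might infer that the devices cannot be compared on AEs at all. Sides are fixed, most expected events are local to the skin, and an event description is collected, so the flank will often identify the device. The AE form is not among the documents, so the absence of a side field on it cannot be shown. What can be said is that the protocol text does not require one.

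**Conclusion.** The point holds as a defect in a stated rule. The two definitions are not mutually exclusive on the literal reading (12 of 16 combinations in both) or on either softer reading tested, and no tie-break is given. The treatment-related AE endpoint is therefore ambiguous, by 10 percentage points for each subject affected at n = 10. How many subjects would be affected cannot be derived from the documents.

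Separately, the listed AE summaries count subjects who each received both devices, and the text requires no attribution by device. They do not serve the stated aim of comparing device safety.

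The documents do not support a conclusion that safety capture or SAE reporting is compromised. The consequence is confined to one safety endpoint in a feasibility study of up to 10 subjects. The verdict rests on reading each *or* in section 8.2.2 at face value and on that section being the only definition of relatedness.

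**What to change.** 1. In section 8.2.2, make the categories exclusive: Not Related only if another cause is established or there is no reasonable possibility of causation; otherwise Related. State that timing alone does not decide.
2. On the AE form, record attribution as LED flank, laser flank, thermocouple procedure or not localised. State whether events attributed to the thermocouple procedure count as treatment-related.
3. In section 10.3, add a table of treatment-related AEs by device.

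The cost is a short rewording, one form field and one table. Two limits remain. The rule resolves most of the overlap towards Not Related: of the 12 combinations now in both categories, 2 become Related (B present, C and D absent, A free) and 10 become Not Related. The sponsor should accept that choice knowingly; taking Not Related as the strict complement of the present Related list would also be exclusive, with 14 combinations Related and 2 Not Related. And in an open-label study, judging a reasonable possibility and an established cause still rests with an investigator who knows the device.

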### 8.2.3 EXPECTEDNESS

Expected adverse reactions are AEs that are common and known to occur for the study agent being studied. Expected adverse events in this study include pain, tenderness, purpura, persistent erythema, edema, burn, blistering, crusting, hyperpigmentation, hypopigmentation, scarring and potential for damage to hair follicles within the treatment area and subsequent loss of hair within the treatment area.

An AE or suspected adverse reaction is considered "unexpected" if it is not known to occur for the study agent being studied and at the specificity or severity that has been observed.

## 8.3 TIME PERIOD AND FREQUENCY FOR EVENT ASSESSMENT AND FOLLOW-UP

The occurrence of an AE or SAE may come to the attention of study personnel during study visits and interviews of a study participant presenting for medical care, or upon review by a study monitor. All AEs including local and systemic reactions not meeting the criteria for SAEs will be captured on the appropriate CRF. Information to be collected includes event description, time of onset, clinician's assessment of severity, relationship to study product (assessed only by those with the training and authority to make a diagnosis), and time of resolution/stabilization of the event. All AEs occurring while on study must be documented appropriately regardless of relationship. All AEs will be followed to adequate resolution.

Any medical condition that is present at the time that the participant is screened will be considered as baseline and not reported as an AE. However, if the study participant's condition deteriorates at any time during the study, it will be recorded as an AE. UPs will be recorded in the data collection system throughout the study.

Changes in the severity of an AE will be documented to allow an assessment of the duration of the event at each level of severity to be performed. AEs characterized as intermittent require documentation of onset and duration of each episode.

The PI will record all reportable events with start dates occurring any time after informed consent is obtained until 7 (for non-serious AEs) or 30 days (for SAEs) after the last day of study participation. At each study visit, the investigator will inquire about the occurrence of AE/SAEs since the last visit. Events will be followed for outcome information until resolution or stabilization.

## 8.4 REPORTING PROCEDURES

### 8.4.1 ADVERSE EVENT REPORTING

All AEs will be recorded on the appropriate CRF and will include information about the start and stop dates, severity and relatedness. There should be an attempt to report a "diagnosis" rather than the individual signs, symptoms and abnormal laboratory values associated with the diagnosis. However, a diagnosis should be reported only if, in the Investigator's judgment, it is relatively certain (i.e., definite or possible). Otherwise individual signs, symptoms and abnormal laboratory values should be reported as distinct adverse events.

### 8.4.2 SERIOUS ADVERSE EVENT REPORTING

All serious AE, whether or not deemed expected or device related, must be reported to the sponsor's clinical research department immediately or within 24 hours by telephone (see contact details below).

Name: [name], Director of Clinical Research

[contact] [name]

Email: [[contact]](mailto:[contact])

Address: [name]

A written report prepared by the Principal Investigator must follow within seven working days to the clinical monitor and should include a full description of the event and sequence.

The study investigator shall complete an a Serious Adverse Event / Serious Adverse Device Effect Form and submit to the study sponsor and to the reviewing IRB as soon as possible, but in no event later than

10 working days after the investigator first learns of the effect. The study sponsor contact information is provided in Section 1, Key Roles. The study sponsor is responsible for conducting an evaluation of an unanticipated adverse device effect and shall report the results of such evaluation to Health Canada, the FDA or local regulatory agency and to all reviewing IRBs and participating investigators within 10 working days after the sponsor first receives notice of the effect. Thereafter the sponsor shall submit such additional reports concerning the effect as Health Canada, the FDA or local regulatory agency requests.

---

#### 8.4.3 UNANTICIPATED PROBLEM REPORTING

Incidents or events that meet the criteria for UPs require the creation and completion of an UP report form. It is the site investigator's responsibility to report UPs to their IRB and to the study sponsor. The UP report will include the following information:

Protocol identifying information: protocol title and number, PI's name, and the IRB project number;

- A detailed description of the event, incident, experience, or outcome;
- An explanation of the basis for determining that the event, incident, experience, or outcome represents an UP;
- A description of any changes to the protocol or other corrective actions that have been taken or are proposed in response to the UP.

An investigator shall submit to the sponsor and to the reviewing IRB a report of any unanticipated adverse device effect occurring during an investigation as soon as possible, but in no event later than 10 working days after the investigator first learns of the effect (21 CFR 812.150(a)(1)). A sponsor who conducts an evaluation of an unanticipated adverse device effect under 812.46(b) shall report the results of such evaluation to Health Canada, the FDA or local regulatory agency and to all reviewing IRB's and participating investigators within 10 working days after the sponsor first receives notice of the effect. Thereafter the sponsor shall submit such additional reports concerning the effect as FDA (21 CFR 812.150(b)(1)) or local regulatory agency requests.

---

#### 8.4.4 REPORTING OF PREGNANCY

If a subject becomes pregnant during the course of the study, the subject will be terminated from the study. The pregnancy will be immediately reported to the sponsor on the Notification of Subject or Partner Pregnancy form and to the IRB using the same reporting timelines as a SAE. The investigator will follow the pregnancy until completion and will report the outcome of the pregnancy to the sponsor on the Notification of Subject or Partner Pregnancy Outcome form and the IRB within 10 business days.

### 8.5 STUDY HALTING RULES

The study may be halted at any time by the sponsor, the IRB, Health Canada, the FDA or local regulatory agencies due to safety concerns. Examples of findings that might trigger a safety review are the number of SAEs overall, the number of occurrences of a particular type of SAE, severe AEs/reactions, or increased frequency of events. If the study is halted, the sponsor will immediately notify all investigational sites, the IRB(s), Health Canada, the FDA or local regulatory agencies.

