### 5.4 PARTICIPANT WITHDRAWAL OR TERMINATION

#### 5.4.1 REASONS FOR WITHDRAWAL OR TERMINATION

Subjects are free to withdraw from participation in the study without prejudice at any time upon request. In the event that a subject drops out of the study or is withdrawn from the study, the Exit/Termination CRF form should be completed. On the withdrawal page, the Investigator should record the date of the withdrawal, the person who initiated withdrawal and the reason for withdrawal.

Reasonable effort should be made to contact any subject lost to follow up during the course of the study in order to complete assessments and retrieve any outstanding data and study medication/supplies. The records of subjects who terminate prior to completing the study will be retained and the reason for termination will be documented.

An investigator may terminate participation in the study if:

- Any clinical adverse event (AE), laboratory abnormality, or other medical condition or situation occurs such that continued participation in the study would not be in the best interest of the subject.
- The subject meets an exclusion criterion (either newly developed or not previously recognized) that precludes further study participation.

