### 5.5 PREMATURE TERMINATION OR SUSPENSION OF STUDY

This study may be temporarily suspended or prematurely terminated if there is sufficient reasonable cause. Written notification, documenting the reason for study suspension or termination, will be provided by the suspending or terminating party to investigator, the investigational device sponsor and regulatory authorities. If the study is prematurely terminated or suspended, the principal investigator (PI) or sponsor will promptly inform the IRB and will provide the reason(s) for the termination or suspension.

Circumstances that may warrant termination or suspension include, but are not limited to:

- Determination of unexpected, significant, or unacceptable risk to participants

- Demonstration of efficacy that would warrant stopping
- Insufficient compliance to protocol requirements
- Data that are not sufficiently complete and/or evaluable
- Determination of futility

Study may resume once concerns about safety, protocol compliance, data quality are addressed and satisfy the sponsor, IRB and/or regulatory authorities.

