#### 7.8 RESCUE MEDICATIONS, TREATMENTS, AND PROCEDURES

In the event that the subject experiences pain, the principal investigator may prescribe any analgesic deemed appropriate to the level of pain. If a subject experiences any first, second or third degree burn or pain beyond narcotics, then the following procedure will be implemented:

Immediate triage and treatment of the patient shall be determined by the treating physician and based upon severity and type of burn identified.

The event will be reported to the study Director within 24 hours of occurrence. If the event meets the criteria of a SAE, then it must be reported on the SAE form.

A copy of the patient chart and treatment parameters are to be forwarded to the study Director within 24 hours.

The study Director will be responsible for issuing a written report to the company and the IRB Chairman no later than 7 days from the incident.

Long term follow up and care shall continue at the discretion of the treating physician.

All patients experiencing a complication of the device will be followed a minimum of 2 years following the initial injury. Longer care and observation will be at the discretion of the treating physician.

All minor complications such as appearance or altered sensation, except for pain, can be reported within 30 days of patient complaint. Both chart and treatment parameters are to be provided to the study Director and shared with the company and IRB chairman.

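### Sections 8.5 and 5.5 give only discretionary power to halt: no burn or SAE, however severe, obliges a hold before the next subject is treated on the same output schedule

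*Combined protocol and SAP*

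**What the plan says.** The operative sentence of Section 8.5 is "The study may be halted at any time by the sponsor, the IRB, Health Canada, the FDA or local regulatory agencies due to safety concerns". It then gives examples of findings that might prompt a safety review: the total number of SAEs, "the number of occurrences of a particular type of SAE, severe AEs/reactions, or increased frequency of events". No count, grade or duty to act is attached. Section 5.5 has the same character: "This study may be temporarily suspended or prematurely terminated if there is sufficient reasonable cause". It lists circumstances, including unacceptable risk to participants, that may justify suspension.

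Several provisions deal with the individual subject. Under Section 5.4.1, "An investigator may terminate participation in the study if" an adverse event makes continuing contrary to the subject's interest. Section 7.8 states: "If a subject experiences any first, second or third degree burn or pain beyond narcotics, then the following procedure will be implemented". That procedure includes triage, a prompt report ("The event will be reported to the study Director within 24 hours of occurrence") and "a written report to the company and the IRB Chairman no later than 7 days from the incident". Section 8.4.2 requires SAEs to be telephoned to the sponsor within 24 hours.

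The exposure is common to all subjects. Section 7.3.2 (Treatment) says "Both laser and LED applicators will be set to same output power level" and fixes two levels, 41 W and 29 W.

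**The concern.** Burns, blistering and scarring are foreseen: Sections 2.3.1 and 8.2.3 list them, and Section 7.8 sets at least 2 years of follow-up for device complications. Because each subject is due the same output schedule, a serious burn in one subject is direct information about the risk to the next. A halting rule normally says in advance which event stops treatment until someone has looked at that information. Here the clearest case, a second- or third-degree burn, obliges no such hold. Whether to pause is decided after the event, without a preset criterion. What is at stake is how many further subjects are treated between a serious event and a considered decision to go on.

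**Working it through.** The plan states no halting threshold or event rate, so there is no figure to reproduce. The check is mainly textual, followed by two short calculations.

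**1. What each provision obliges**

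| Provision | Obligation | Requires a hold on the next subject? |
|---|---|---|
| 7.3.2 Treatment, intolerable pain | That treatment must stop | No |
| 7.3.2 Assessment | Skin examined and graded at 30 minutes | No |
| 5.4.1 | Investigator may end that subject's participation | No |
| 7.8, any burn | Triage, 24-hour report, written report within 7 days, follow-up | No |
| 8.4.2, SAE | Telephone report within 24 hours, then written reports | No |
| 8.4.3, unanticipated problem | Report describing protocol changes or corrective actions taken or proposed | No; actions are described, none is required |
| 8.6 | Oversight by the sponsor and a medical monitor | No action specified |
| 5.5 and 8.5 | Suspension or halt permitted | Permitted, not required |

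The reporting routes overlap only partly for burns. A burn that needs intervention to prevent permanent impairment is an SAE under Section 8.1.2. Burn is an expected event in Section 8.2.3, so whether a given burn is also unanticipated under Section 8.1.3 depends on its severity or frequency. No route ends in a required pause.

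**2. Timing**

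Inputs: up to 10 subjects and up to two months (Section 5.3), taken as 60 days; burn reports at 24 hours and 7 days (Section 7.8).

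- Even pace: 60 / 10 = 6 days per subject. Further subjects treated before the 24-hour report is due: 1 / 6 = 0.2. Before the 7-day report: 7 / 6 = 1.2.
- Fastest pace the text leaves open: two 24-minute treatments and the 30-minute examination take 24 + 24 + 30 = 78 minutes. An assumed 8-hour day gives 480 / 78 = 6.2, so 6 subjects, ignoring set-up. Section 7.3.2 also gives components of 4 + 16 = 20 minutes; on that reading 20 + 20 + 30 = 70 minutes and 480 / 70 = 6.9, still 6. If the first were burned, up to 5 more could be treated before the 24-hour report is due.

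**3. How often the proposed pause would occur (illustration only)**

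Let p be the assumed chance that a subject has a triggering event on either flank. Assume subjects are independent, are treated in sequence, and each event is known before the next subject.

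- Chance of a pause before the 10th subject: 1 − (1 − p)^9.
- Mean number of subjects still to be treated after a first event, counting studies with no event as zero: 10 − [1 − (1 − p)^10] / p.
- The same mean among studies with at least one event: divide by 1 − (1 − p)^10.

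| Assumed p | Chance of a pause | Mean still to be treated, all studies | Chance of at least one event in 10 | Mean still to be treated, given an event |
|---|---|---|---|---|
| 0.01 | 0.087 | 0.44 | 0.096 | 4.6 |
| 0.02 | 0.166 | 0.85 | 0.183 | 4.7 |
| 0.05 | 0.370 | 1.97 | 0.401 | 4.9 |
| 0.10 | 0.613 | 3.49 | 0.651 | 5.4 |

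Example at p = 0.05: 0.95^9 = 0.630, so the chance of a pause is 0.370. 0.95^10 = 0.599, so 10 − 0.401 / 0.05 = 1.97, and 1.97 / 0.401 = 4.9.

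The last column counts subjects whose treatment would wait for a review. It is not exposure averted, because treatment may resume.

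**The case against.** The strongest reply is that the study is well protected for its size. It has up to 10 subjects at one site, one session each, water-cooled applicators and a non-significant-risk determination (Section 2.2). Intolerable pain must end treatment, which for a heating device is a direct limit on a burn in progress. The investigator examines the skin at 30 minutes, so whoever sees an early burn is at the site where the next subject is treated, and Section 5.5 contemplates the investigator's involvement in a suspension. Burns and SAEs are reported within 24 hours, so a discretionary halt could follow quickly. All of this stands and lowers the expected harm. It does not supply a required hold.

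A reader might infer three stronger points that the documents do not support.

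- That the decision waits for the 7-day report or rests with the sponsor alone. The 7-day report is the slowest channel, and the investigator knows sooner.
- That the medical monitor lacks power to pause or is left off the reports. Section 1 (Key Roles) and the Monitoring Plan were not available for this review, so silence in the remaining text proves nothing.
- That subjects will be treated several per day. No interval between subjects is set, but the plan anticipates up to two months. Requiring the previous 30-minute examination first would not change the fast scenario, which already includes that wait.

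**Conclusion.** The point holds as a low-cost safety improvement. In the text available, no burn or SAE obliges a study-level hold, and this conclusion needs no assumed event rate. At the anticipated pace the practical size is about 1.2 further subjects before the written burn report is due; the fast schedule is a possibility left open, not the plan.

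The pause probabilities rest wholly on assumed risks, on independence between subjects and on immediate detection. They are best-case figures: burns that appear after the 30-minute examination may be found only after later subjects have been treated.

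A reader might take the finding as evidence of unsafe conduct or of a flaw in the primary result. Neither follows. Likely harm is limited, and a pause rule has no bearing on the validity of the temperature comparison.

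**What to change.** Add to Section 8.5: after any device-related second- or third-degree burn, or any device-related SAE, on either flank, no further subject is treated until the medical monitor (or the sponsor's designated safety reviewer) has documented a review and a decision to resume, with settings unchanged or modified. State that burns count even though Section 8.2.3 lists them as expected, that the transient erythema and edema Section 7.3.2 calls normal do not count, and that the discretionary powers in Sections 5.5 and 8.5 remain.

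A further trigger based on a count of first-degree burns is optional. If the sponsor wants one, it should be fixed before the first treatment.

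The cost is one short amendment and, for each triggering event, one review and a possible short delay in a two-month study. No extra visits, procedures or subjects are needed.
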